1. STUDY DESIGN

The study design was chosen according to the current standards required by ISO, GCP and according to national requirements.

- a. A Parallel-Arm, Statistician is blinded, RCT will be established;
- b. The RCT will be run as mono-center;
- c. A total of 40 subjects will be recruited to participate in the study. It is expected that all of 34 subjects will complete the study in total;
- d. Admission into the study will be via rolling admission (estimated recruitment time: 12 months);
- e. Each subject must have posterior monoedentulia (mandibular or maxillary) intercalated;
- f. Each subject will follow the following treatment protocol:
 1. Visit 1: (Screening)
 - a. Screening and entry into study.
 - b. Verification of the eligibility of each subject by performing intraoral radiography.
 - c. Explanation of the research protocol.
 - d. Consent secured.
 - e. Delivery of the medical request for CBCT (cone beam computed tomography) and for the antibiotic (Amoxicillin 1000mg 2cp/die every 12 hours for 6 days or Azithromycin 500mg 1cp/die every 24 hours for 6 days).
 2. When CBCT is ready the patient have to give it to the Principal Investigator to confirm the eligibility of each subject and to plan the surgery. Professional dental hygiene session is performed before surgery.
 3. Visit 2: (Treatment)
 - a. Assessment of antibiotic prophylaxis, locoregional anesthesia and opening of a thickness flap limited to the intervention area.
 - b. According to the list of randomization the patient will be allocated into one of the two arm of surgical treatment. Group A (control group): placement of the endosseous crestal implant through dedicated drills with 35N insertion torque and healing abutment. Group B (test group): placement of the endosseous subcrestal implant (2 mm under crestal bone) through dedicated drills with 35N insertion

torque and GFA (Gingival Former Abutment). Both group receive the same implant: TZero® (L= 9 mm, Ø 3,6 mm or L= 7,5 mm, Ø 4,3 mm) (Advan S.r.l. [name])

- c. Suture.
- d. Execution of intra-oral and post-operative X-Rays.

After 7 days of the surgery suture removal.

- 4. Visit 3: (after 3 months from visit 2) (Treatment)
 - a. Periodontal charting around the healing abutment or GFA (PD, BOP, PI) with calibrated periodontal probe.
 - b. Impression taking for prosthetic finalization.
- 5. Visit 4: (after a week from Visit 3: Baseline – T0): (Treatment)
 - a. Prosthetic finalization and loading.
 - b. Periodontal charting around the new prosthetic crown (PD, BOP, PI, REC).
 - c. Take a standardized x- Ray (Bite Block).
- 6. Visit 5 (6 months from baseline – T1): (Follow-up)
 - a. Control.
 - b. Periodontal charting around the prosthetic crown (PD, BOP, PI, REC).
 - c. Take a standardized x- Ray (Bite Block).
 - d. Professional dental hygiene session.
- 7. Visit 6 (12 months from baseline – T2):
 - a. Control.
 - b. Periodontal charting around the prosthetic crown (PD, BOP, PI ,REC).
 - c. Take a standardized x- Ray (Bite Block).
 - d. Professional dental hygiene session.
- g. All treatments are made by the same clinician;
- h. Data collection:
 - Standardized X- Ray: control periapical radiographs is performed using a long-cone paralleling technique and an individual X-ray holder (bite block) to ensure reproducibility. Built thanks to impression material.
 - A calibrated periodontal probe (Click-Probe™ Kerr Dental) is used on six sites per tooth (mesio-buccal, buccal, disto-buccal, mesio-lingual, lingual and disto-lingual) with a standard probing force by the same clinician. Measurements are rounded to the nearest millimeter;

- j. Clinical and radiographical assessment data will be recorded via hard copy CRFs. CRFs will be submitted to a data entry staff member for entry into the statistical database. At the conclusion of the study, such statistical database will be submitted to the statistician for the preparation of the statistical analysis and the final study report.
- k. Prosthetic finalization is given to the dental laboratory.

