- Good oral health (no decay, periapical or periodontal lesions, PI and BOP < 25%).
- Patient with posterior monoedentulia:
 - at least 5 months,
 - mandibular or maxillary,
 - intercalated (distance between teeth more than 7.5 mm),
 - at least 11 mm of height residual bone (from bone crest to maxillary sinus or inferior alveolar nerve),
 - at least 5 mm of bone width (buccal – palatal/lingual).
- Availability for the 12-month duration of the study for an assigned subject.

Exclusion Characteristics

- Not willing to follow the agreed protocol.
- Presence of orthodontic appliances.
- Smokers more than 10 cigarettes per day.
- Chronic obstructive pulmonary disease and asthma.
- Tumors or significant pathology of the soft or hard tissues of the oral cavity.
- Current radiotherapy or chemotherapy.
- Pregnant or lactating women.
- Parafunctions like bruxism.
- Previous interventions to increase bone thickness in the implant area.
- Current or past assumption of medications that may influence surgical therapy and/or interfere with healing following surgical treatment.
- Systemic diseases that constitute a contraindication to surgical therapy and/or interfere with healing following surgical treatment.

A written informed consent will be obtained from each included patient after explanation of the risks and benefits of participating to this study. No change in the trial design will be made after approval of the Ethical Committee.

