3. PROCEDURE

Screening and Selection of Subjects

Patients visiting the U.O. Odontostomatology of ASST Spedali Civili of Brescia will be asked to participate in this study. Subjects will report to the clinical facility and be screened by the dental examiner to identify those subjects who meet the inclusion/exclusion characteristics. The findings of this initial screening procedure will be recorded on the CRF. Subjects who meet the inclusion/exclusion characteristics and sign an Informed Consent Form will be entered into the study.

Baseline Oral Soft and Hard Tissue Assessment

All subjects will receive an evaluation of their oral soft and hard tissues. This examination will include an evaluation of the soft and hard palate, gingival mucosa, buccal mucosa, mucogingival fold areas, tongue, sublingual and submandibular areas and the tonsillar and pharyngeal areas. The results of this evaluation will be recorded on the CRF.

CBCT

All patients receiving a CBCT to confirm the eligibility of each subject and to plan the surgery at Complex Operative Unit of Diagnostic Radiology 2.

Treatment

Patients who have been identified for treatment receive an implant placement and prosthetic finalization will be randomized according to a randomization table generated.

Clinical Periodontal Evaluation

All patients receiving treatment will be evaluated by the dental examiner for the following assessments (see Study Flow Chart):

- Full Mouth Plaque Score (PI);
- Periodontal Inflammation (BOP);
- Probing Pocket Depth (PD);
- Recession (REC);

All parameters will be recorded in the CRF.

Radiographically Evaluation

All patients receiving control reproducible periapical radiographs for evaluation of MBL (mesial and distal) (see Study Flow Chart)

All parameters will be recorded in the CRF.

Follow up

Following completion implant placement and prosthetic finalization, the study start. Radiographically and clinical evaluation will be done at baseline (T0), 6 and 12 months (T1 and T2) in the test and control site. At 6 and 12 months a dental hygiene session and OHI will be done.

Study Flow Chart

Study phase	Enrolment	Treatment	Treatment	Treatment	Follow-up	Follow-up
Study visit	Visit 1	Visit 2	Visit 3	Visit 4 (T0)	Visit 5 (T1)	Visit 6 (T2)
Study Time	- X days	0	3 months	3 months and 1 week	6 months from visit 4	12 months from visit 4
Selection criteria	+					
Informed consent	+					
Demographics, ethnics	+					
General health status	+	+	+	+	+	+

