4. STATISTICAL ANALYSIS

Sample size determination

Sample size was compute assuming a two parallel groups design with balanced groups and an independent sample t-test. We assumed a single implant and a single measurement for patient, a standard deviation of 0.5 mm and an average difference of at least 0.5mm. A total sample size of 34 patients will provide a power of at least 80% at a 5% significance level. Assuming a 15% drop-out , the total sample size will be N=40 patients.

Statistical Analysis

Data will be described using standard statistics such as, mean, median standard deviation and IQR for quantitative variable, and counts and percentages for qualitative variables.

Variation in MBL will be modelled using both a simple t-test for independent samples (after averaging values within patients) as well as a multilevel model using GEE (Generalised Estimating Equations) on individual site measurements and accounting for within subject correlation.

Secondary continuous outcomes will be modelled using GEE with ad hoc error distribution according to outcome (Gaussian for PPD, CAL, REC, binomial for BOP).

Results will be expressed as estimates and relative 95% confidence intervals. A significant level of 5% will be used for all the comparisons and all analysis will be performed using R (version 3.6.3 or higher).

Evaluation of Safety

The following safety variables will be used for the evaluation of safety:

- Adverse events (AE);
- Adverse reactions (AR).

The total number of AEs and the total number of AEs at least possibly related to the study treatment, as well as the total number of patients affected by at least one adverse event will be calculated per treatment group.

The type of AE classified by organ system (according to MedDRA terminology) will be tabulated. Serious and/or unanticipated adverse events and AEs resulting in discontinuation or reduction/withdrawal of the study treatment will be presented separately.

Safety analysis set

Safety summaries will be based on the safety analysis set which will consist of all patients who received the test/control treatment.

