11. ETHICAL ASPECTS AND REGULATIONS

Ethical Conduct of the Study

This study is to be conducted in accordance with the ethical principles of the Declaration of Helsinki and according to local laws and regulations.

Independent Ethics Committee (IEC) and Relevant Authorities

Before starting the study, the study protocol will be subject to review by the Ethical Committee of the University-Hospital of Brescia. As required by law, the study will be notified to authorities if applicable. No subject should be admitted to the study before the Ethical Committees issue their written favourable opinion of the study. Periodic status reports must be reported to the ethics committee at least annually as well as notification of the completion of the study. The investigator must maintain an accurate and complete record of all reports and documents submitted to and received from the ethics committee according to the ISO 14155:2011 Clinical Investigation of Medical devices for human subjects.

Subject information and Informed consent form

The purpose and description of the study in lay language, possible adverse reactions, risks and benefits of participation and the subject's right to withdraw without prejudice at any time must be explained to each subject. Each subject must read, understand and sign the informed consent form provided before any study-related procedure.

Subject data protection and Confidentiality

The name of the subject as well as all other personal data will be kept strictly confidential by the Investigator. If due to medical reasons, it is necessary to identify the subject during the study course, this will be done under medical secrecy.

The subject has given his/her consent before the beginning of the study. In case of withdrawal of this consent subject has to leave the study.

All subjects will agree to verify, by letter, that they participated in this study, if called upon to do so.

New Findings

Subjects will be informed of any significant new findings related to study products or procedures when they become known during the course of this clinical research study. Such information may affect the subject's decision to continue participation in the study.

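### The Visit 1 list places study entry and the eligibility radiograph before explanation and consent, which contradicts the consent rule in Section 11

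*Combined protocol and SAP*

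**What the plan says.** Section 1 (Study Design) sets out Visit 1 as five lettered items:

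- Item (a) opens the visit and already covers entry: "Screening and entry into study"
- Item (b) is the eligibility film: "Verification of the eligibility of each subject by performing intraoral radiography"
- Item (c) is where the trial is explained to the patient.
- Item (d) is the consent step: "Consent secured"
- Item (e) is where the requests for the CBCT and the antibiotic are handed over.

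Section 11 (Subject information and Informed consent form) gives the rule on timing: "Each subject must read, understand and sign the informed consent form provided before any study-related procedure".

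Three other places touch on consent:

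- Section 3 (Screening and Selection of Subjects) describes screening by the dental examiner and then says: "Subjects who meet the inclusion/exclusion characteristics and sign an Informed Consent Form will be entered into the study".
- The paragraph after the exclusion criteria says: "A written informed consent will be obtained from each included patient after explanation of the risks and benefits of participating to this study".
- The Study Flow Chart marks selection criteria, informed consent and X-rays all under Visit 1.

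**The concern.** The visit list is the text that clinic staff follow on the day. As printed, it puts a radiograph, taken to establish whether someone qualifies for the trial, ahead of both the explanation of the trial and the signature. Section 11 requires the signature first.

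What is at stake is participant protection. Those most exposed are people who decline after the explanation or who turn out to be ineligible: they could have had an X-ray for the trial's purposes without having agreed to take part. People who go on to enrol would have had the film before signing. The radiation from an intraoral film is not the main issue. The issue is that the protocol's operational instruction and its own consent rule cannot both be followed as written.

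**Working it through.** The protocol gives no figure on this point, so the check is a comparison of texts.

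1. **Order in the visit list.** Entry is (a), the radiograph (b), explanation (c), consent (d), and the CBCT and antibiotic requests (e). The radiograph is therefore printed one place before explanation and two places before consent.

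2. **Is the radiograph study-related?** Its stated purpose is to verify eligibility, and the wording is that a radiograph is performed, not that an existing one is reviewed. The flow chart also schedules X-rays at Visit 1. On the protocol's own wording it falls under the Section 11 rule. Nothing in the documents describes it as routine care, as a pre-existing image, or as covered by a separate screening consent.

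3. **Is the list a time sequence?** Items (b) to (e) read as one: explanation leads to consent, consent comes before the CBCT request, and the next numbered step begins once the CBCT is available. Item (a) does not fit. Section 3 allows entry only for people who both meet the criteria and sign, and a signed consent form is itself the first inclusion criterion, so entry cannot come before (b) or (d). The list is therefore loosely ordered in at least one place, and entry is a second item printed ahead of consent.

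4. **Does another section settle the order?**
   - Section 3 mentions no radiograph in its screening paragraph. It sets a joint condition for entry and does not say when signing happens relative to screening procedures.
   - The paragraph after the exclusion criteria requires consent from included patients, after explanation. It gives no timing relative to screening and does not speak of people who are not included.
   - The flow chart puts everything in one Visit 1 column, without order.
   - No clause says that Section 11 prevails over the visit list.

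5. **What is not affected.**
   - The CBCT request, item (e), follows consent on any reading.
   - The baseline for marginal bone level is T0 at Visit 4, which is 3 months and 1 week after surgery, so the screening film does not enter the primary outcome.
   - The sample size in Section 4 rests on "a standard deviation of 0.5 mm and an average difference of at least 0.5mm" and on a 15% drop-out, and uses nothing from screening.

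**The case against.** The strongest reply is that Section 11 already contains the right rule, clearly stated, and that a site obeying it would never take a study film before signature. On this view item (a) works as a title for the visit, the letters (b) to (e) are contents and not a timetable, and all that remains is untidy drafting. Candidates are also patients attending the hospital's odontostomatology unit, where an intraoral film may be part of ordinary work-up.

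Much of this stands. The protocol does not lack a consent safeguard, the letters are not declared to be chronological, and the film may be routine. What does not stand is the conclusion that nothing needs changing. A general clause near the end of the protocol does not correct a contrary step list in the design section, and if the film is routine care the protocol should say so.

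A reader might also infer more than the documents support:

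- **That patients will be irradiated for research without consent, in every case.** This assumes strict chronology, a new film for everyone and no clinical indication, and none of these is stated.
- **That Section 3 repeats the same order for the radiograph.** Its screening paragraph does not mention one.
- **That screening data would be unusable.** No text supports this.
- **That the consent form itself is deficient.** The form is not in the text available for review, so nothing can be concluded about it.

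**Conclusion.** The point holds as an internal contradiction with a limited consequence. The Visit 1 list prints entry and the eligibility radiograph before explanation and consent, and Section 11 requires the reverse. If the list is followed as printed, people who decline or fail screening could receive an intraoral X-ray for eligibility before consenting.

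The size cannot be given as a count. The protocol plans 40 randomised patients but states no number screened, declining or failing screening. The conclusion rests on two assumptions: that staff may read items (b) to (e) as a sequence, and that the film is taken for the trial, as its stated purpose implies. If either is wrong, no one is exposed before consent for the trial's sake, but the text would still need correcting. There is no effect on the endpoints, the sample size, the significance level or the analysis. This is a minor correction, but worth making.

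**What to change.** In Section 1, Visit 1, put explanation of the protocol and signed consent first, followed by the eligibility radiograph, and place entry into the study after both. In the Section 3 screening paragraph, add a sentence saying that consent is signed before any screening procedure done specifically for the study. If the radiograph is in fact part of routine work-up, say so explicitly in the same place.

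The cost is small. Section 9 requires a protocol amendment with prior approval, so this is slightly more than an editorial change. Some people who sign will then fail screening on the radiograph. That is not new in kind, because the plan already confirms eligibility on the CBCT after consent.

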2. TREATMENTS

Implant kit, implants and every component will be delivered to the study center prior study start by Advan S.r.l. [name]:

- Surgical Kit PRO: GKC13
- Set countersink GFA: GKM10
- Kit stop drills: GST11
- Implant: TZero - T3609 (D3,6 L9,0) - T4307 (D4,3 L7,5)
- GFA: 04GFX03 (D4,0 H3,5) - 04GFX04 (D4,0 H4,5) - 04GFX05 (D4,0 H5,5)
- component GFA: 01GFT01 (healing stopper H1) - 01GFT03 (healing stopper H3) -01GFT05 (healing stopper H5) - 01TGF10 (transfer pick-up) - 01AGF10 (analogo GFA) -01CGF40 (moncone calcinabile con base in cobalto-cromo)
- for control group: 05OMG12 (healing abutment H2) - 05OMG13 (healing abutment H3) - 05OMG14 (healing abutment H4) - 01OTR10 (transfer pick-up) - 41CCN40 (moncone calcinabile con base in cobalto-cromo)

Radiographically Analysis

Specification of software analysis

Peri-apical x-ray examinations will be performed using phosphor image plates (FONA™ Dental Image Plates) and then acquired through a digital scanner device (FONA ScaNeo™).

All radiographical images will be later analyzed by the same external examiner, which will measure marginal bone level parameter (MBL) around placed endosseous implants using an image analysis software (ImageJ™).

In particular bone levels will be determined, both mesially and distally the dental implant, using the “Measure” function of the software, which records the distance between the most apical bone point and the most coronal bone point in 0.3 mm range from the implant.

Measurements will be all recorded to allow the observation of bone level changes over time.

Concomitant Therapy

A necessary concomitant medication or therapy is permitted as long as it is not excluded in the exclusion criteria. Every medication has to be reported in the CRF (Appendix 1) and in the Concomitant Medication form (Appendix 2). All changes during the study are to be reported in the CRF. Usage of prohibited therapy will lead to the exclusion of the subject.

Blinding and Randomization

Blinding:

The statistician and the patient will be blinded to the group identification. The operator will know the treatment allocation. Knowledge of the randomization list will be limited to the persons responsible for creation of the randomization list, provider of randomization numbers to study site, and delivery of the test/control treatment until the last subject (i.e. final examination of the last subject), quality control and verification of the CRFs is completed.

Randomization and allocation concealment:

The randomization of the study protocols will be performed by a staff member who is not further involved in this study. This will be done based on a computer-generated table (using R package *randomizeR*) that links each patient to one of the treatment groups. Treatment allocation will be delivered in sealed envelopes.

Implementation: The Principal Investigator will be informed immediately of Serious Adverse Events (SAEs), regardless of the causality relationship between the administration of the investigational treatment and the SAE.

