CONFIDENTIAL AND PROPRIETARY

Information provided herein is the property of the University-Hospital of Brescia. Nothing herein is to be reproduced, published, or disclosed to others in any way without the prior expressed written permission of the University-Hospital of Brescia.

Title of Study: The role of a new prosthodontics device in hard and soft tissue changing after subcrestal implant placement: 12 months parallel randomized clinical trial.

Type of Study: Clinical

Protocol No: PROTOCOL NABUT2020

Expected study start date: September, 2020 (study initiation)

Study Location/Country: Brescia, Italy

Study Originator(s)/ Contact (name, phone, fax): [name], [name], [contact], email: [contact]

Test Products w/ PDM Numbers:

CE marked Medical Device to be used as a prosthodontics device after subcrestal implant placement in patients with monoedentulia (Confidential information).

Study Title:	The role of a new prosthodontics device in hard and soft tissue changing after subcrestal implant placement: 12 months parallel randomized clinical trial.
Study sites:	[name] (lead site) University-Hospital of Brescia Brescia, Italy.
Study Phase:	IV.
Name of Medical Device:	GFA® Gingival Former Abutment (Advan S.r.l. [name])
Objective:	The objective of the clinical study is to assess the efficacy of a new prosthodontics device (GFA) in hard and soft tissue changing after subcrestal implant placement.
Patient Population:	40 patients, systemically healthy, male and female adults (18 – 75 years), with posterior monoedentulia at least 5 months.
Structure:	Parallel arms: Number of treatments: 1 (test group: subcrestal implant placement and GFA; control group: crestal implant placement and healing abutment).
	Duration of study: 27 months.
Number of Centers:	One.
Blinding:	Statistician
Method of Patient Selection:	Posterior monoedentulia intercalated with 11mm of residual bone
Total Sample Size:	40 adult subjects will be recruited (randomized) to participate in this study, with 34 expected to complete the study.
Primary Efficacy Variable:	Primary outcome measure will be the changing of radiographically MBL (marginal bone level) around implant.

**The role of a new prosthodontics device in hard and soft tissue changing after
subcrestal implant placement: 12 months parallel randomized clinical trial.

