
At present there is no scientific evidence in dentistry about the origin and treatment of perimplatitis and mucositis. These peri-implant pathologies can be partially prevented through periodontal diagnosis, correct implant placement and prosthetic loading.

In the literature, there is a physiological bone loss around implant after the placement (1 mm the first year and 0.2 mm each subsequent year). Different types of implants have been designed (laserization of the collar, platform switching..) to try to control this phenomenon with discordant results. Different surgical protocols for implant insertion have been created to minimize bone resorption: a subcrestal implant seems to partially overcome this problem even if this procedure increase the transmucosal tunnel: growing the risk of peri-implant soft tissue infection.

Tissue healing around the implants is not comparable to the natural dental element: the risk of inflammation and consequently of infection is higher around the implants because there is no stable seal between the two structures (tissue and implant).

The prosthetic structure of the GFA was created to overcome these problems: crestal bone reabsorption and transmucosal tunnel. Our objective is to validate or deny this claim.

STUDY OUTCOMES

- a. Primary outcome measure: radiographically change in MBL
- b. Secondary outcomes changes in the following clinical parameters:
 - PD (Probing Depth),
 - REC (Clinical Gingival Recession),
 - BOP (Bleeding on Probing),
 - PI (Plaque Index).

STUDY POPULATION

Forty (40) adults, aged 18-75 years, will be entered into study (randomized). It is expected that forty (34) subjects will complete the study.

Randomized subjects who deviate from the protocol (major protocol deviation) and, for this reason, are excluded from the analysis, will be replaced to guarantee that the sample required for the analysis (34) is reached.

Patients will be treated at the Department of Surgical Specialties Radiological Science and Public Health, School of Dentistry, Section of Periodontics, Brescia, Italy from 09/2020.

Inclusion Characteristics

- Comprehension and signed Informed Consent Form.
- Male and female subjects, aged 18-75 years, inclusive.
- Good general health (free of systemic diseases such as diabetes, HIV infection or genetic disorder, ongoing malignant disease of any type that could influence the outcome of the treatment and might interfere with the evaluation of the study objectives).

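### The only working definition of the primary endpoint, MBL, runs between two bone points: it has no fixed implant reference and no rule for bone above the implant shoulder

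*Combined protocol and SAP*

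**What the plan says.** The synopsis names the endpoint without defining it: "Primary outcome measure will be the changing of radiographically MBL (marginal bone level) around implant". Study Outcomes repeats the label. Section 3 adds only that MBL is read mesially and distally. Section 4 says only that variation in MBL is averaged within patient for a t-test and modelled by site with GEE.

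The working definition is the ImageJ instruction in section 2, Radiographically Analysis, which "records the distance between the most apical bone point and the most coronal bone point in 0.3 mm range from the implant". The next sentence gives the purpose: "Measurements will be all recorded to allow the observation of bone level changes over time".

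The arms differ in vertical position. Section 1, Visit 2, puts the control implant at the crest, and the test arm has "placement of the endosseous subcrestal implant (2 mm under crestal bone". The implant itself is common to both: "Both group receive the same implant".

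Two safeguards concern the films and their reading. Section 1 specifies a "long-cone paralleling technique and an individual X-ray holder (bite block) to ensure reproducibility", and section 2 states that "All radiographical images will be later analyzed by the same external examiner".

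**The concern.** A bone level needs an origin that does not move. Here the implant only limits how far to the side the examiner looks (0.3 mm); it sets no vertical zero. No section names a shoulder, platform, apex or other landmark, a sign convention, or a way to score bone beside the abutment.

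Two things are at stake. First, a distance between two bone points does not change when both move together, so real loss, and a real difference between arms, can go unrecorded. Second, bone above the shoulder is expected by design in the test arm only. Whether it counts can therefore affect the arms differently, and the plan leaves that to the examiner.

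**Working it through.** **The plan's own figure.** Inputs from section 4: difference 0.5 mm, SD 0.5 mm, 5% significance (two-sided assumed), two equal groups, t-test. The exact noncentral t calculation needs 16.7, so 17 per arm, or 34 in total, with power 80.7%. With 15% drop-out, 34 / (1 − 0.15) = 40. The stated sample size reproduces and is not in question.

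**The section 2 rule on simple cases.** Positions are assumed for illustration, with shoulder = 0 mm and coronal positive. Distance = coronal point − apical point.

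| Case | Apical point | Coronal point | Change in distance | Change in coronal point from shoulder | Change in apical point from shoulder |
|---|---|---|---|---|---|
| Control, even loss | 0 to −0.5 | 0 to −0.5 | 0.0 | −0.5 | −0.5 |
| Test, even loss | +2.0 to +1.5 | +2.0 to +1.5 | 0.0 | −0.5 | −0.5 |
| Crater forms, crest stable | 0 to −0.5 | 0 to 0 | +0.5 | 0.0 | −0.5 |
| Crest loss flattens that crater | −0.5 to −0.5 | 0 to −0.5 | −0.5 | −0.5 | 0.0 |

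The distance rises as a crater forms. In the last row it falls, so further loss reads as a gain.

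**Dilution under the literal reading.** Let h be the share of loss that is even, assumed the same in both arms. A true 0.5 mm difference then reads as 0.5 × (1 − h): 0.5 mm at h = 0, 0.25 mm at h = 0.5, 0 mm at h = 1. With SD still 0.5 mm and 17 per arm, power when 100%, 75%, 50% or 25% is captured is 80.7%, 56%, 29% or 11%. The documents give no h.

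**Bone above the shoulder.** In the second row, if readings were cut at zero, both +2.0 and +1.5 would score 0, so 0.5 mm of loss would read as none. The same loss in control would be recorded.

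To size this, assume that patient loss x is Normal with mean μ and SD 0.5 mm in both arms, so there is no true effect. Let c be the bone above the test shoulder at T0, and take the control crest as flush. The test arm reads max(0, x − c), with mean (μ − c)Φ((μ − c)/0.5) + 0.5φ((μ − c)/0.5). The control arm reads max(0, x) under the same cut, or x if nothing is cut there. At μ = 0.5 its mean is 0.542 or 0.500 mm.

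Example at c = 0.25: 0.25 × 0.691 + 0.5 × 0.352 = 0.349 mm, so the spurious difference is 0.500 − 0.349 = 0.15 to 0.542 − 0.349 = 0.19 mm.

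| μ (mm) | c (mm) | Test mean (mm) | Spurious difference (mm) | Simulated trials with p < 0.05, 17 per arm |
|---|---|---|---|---|
| 0.5 | 2.0 | 0.000 | 0.50–0.54 | 97.6% to over 99.9% |
| 0.5 | 1.0 | 0.042 | 0.46–0.50 | 93.8–99.8% |
| 0.5 | 0.5 | 0.200 | 0.30–0.34 | 54.9–74.8% |
| 0.5 | 0.25 | 0.349 | 0.15–0.19 | about 18–27% |
| 0.5 | 0, cut in both arms | 0.542 | 0 | about 5% |
| 0.2 | 2.0 | 0.000 | 0.20–0.32 | 36.8–99.6% |

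The upper end of each range cuts both arms alike; the lower end leaves control uncut. No reading error is included. With an assumed reading-error SD of 0.3 mm, the first row falls to 86–96% and the third to 39–53%. If all bone is counted in both arms, the spurious difference is 0 in every row.

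Neither μ nor c can be taken from the plan. The Introduction says "there is a physiological bone loss around implant after the placement (1 mm the first year and 0.2 mm each subsequent year", but that runs from placement, whereas T0 is Visit 4, 3 months and 1 week after surgery. The 2 mm depth likewise describes surgery, not T0.

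**The case against.** A reader might infer that the plan builds in a false benefit for the test device. The documents do not support that. The bias arises only if readings stop at the shoulder. Section 2 asks for the most coronal bone point and mentions no cut, so the cut is a possible reading and not a stated rule. Its size also depends on bone cover at T0 and on reading error, both unknown; at 0.25 mm of cover the effect is modest, and at 0 mm it vanishes.

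Nor do the documents support a specific loss of power. The dilution figures run from none to complete, according to an unknown h that is assumed equal in both arms.

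It is also fair to say that section 2 speaks of bone levels and their change over time, which suggests a level measurement that was badly worded rather than an intended defect-depth endpoint. One might take the apical point to mean first bone-to-implant contact. The text does not say so, and the other end of the distance would still be a bone point that moves.

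The single external examiner and the bite-block films do limit reader and projection variation. They do not supply an origin: a reading that depends on implant depth would be repeated consistently and would stay biased. Averaging sites or using GEE cannot restore a missing reference either.

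Finally, measuring only to the most coronal bone would have its own blind spot. A defect against the implant narrower than 0.3 mm, with a stable crest inside the band, would read as no change, as the third row of the first table shows. The fix allows for this.

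**Conclusion.** The point holds and should be settled before any film is read. The sole primary endpoint has one operational definition, and followed as written that definition can give a wrong answer: even loss reads as none, and a flattened crater reads as a gain. This conclusion rests on the wording alone and needs no assumed figure.

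The direct consequence is possible dilution of a true difference between arms, of a size the documents do not let us estimate. A spurious test-arm benefit is a conditional risk only. It needs readings cut at the shoulder, ranges from zero to about the full 0.5 mm planning difference in the cases tried, and is absent if all bone is counted. The sample size of 34 evaluable and 40 randomized patients is unaffected unless the SD of the redefined measure differs from 0.5 mm.

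**What to change.** Before any film is read, replace the distance sentence in section 2 with one rule for both arms:

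- **Origin:** the shoulder of the common TZero implant, read mesially and distally.
- **Bone point:** one named point chosen by the investigators, for example first bone-to-implant contact, or the most coronal bone within the 0.3 mm band.
- **Sign:** vertical distance from the shoulder, positive above and negative below, with bone above the shoulder counted and not cut at zero.
- **If most coronal bone is chosen:** also record the deepest bone point from the same shoulder reference, so that narrow defects are not missed.

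In section 4, state that variation in MBL is the T2 value minus the T0 value on this scale, so that a negative result means loss.

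The cost is a revised reading instruction and one sentence in section 4, with the same films, examiner and software and no extra visit or patient. The downside is that the shoulder must be visible on each film, and there is a little more reading work.
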